### **Psychosocial Function**

**Depression**- Two standardized, clinical measures of depression will be administered to all participants.

- **Geriatric Depression Scale-15** (GDS) will evaluate depression in oldest old adults, and has demonstrated high specificity, and predictive value for older adults (Yesavage et al., 1988).
- **Beck Depression Inventory II**- recommended by the American Academy of Neurology, and suitable for screening individuals with PD. A cutoff of 18 is reliable for distinguishing individuals with PD with significant depression.

**Incontinence (self-report): ICI-Questionnaire**-this questionnaires asks four questions pertaining to how often someone urinates during the day, during the night, whether they have a sudden urge to go to the toilet to urinate, and whether they experience leakage right after feeling that sudden urge. Participants are also asked to rate how much each occurrence bothers them on a scale of 0-10 (0 meaning not at all, 10 meaning a great deal).

**Balance confidence**: Activities-specific Balance Confidence scale (ABC; Whitney et al., 1998). This questionnaire is filled out by the participant and asks 16 questions related to confidence the participant would feel about “not losing their balance” in various life situations.

#### **Quality of life:**

- **Short Form -12**- a widely used measure of general health.
- **Life Space Questionnaire** (LSQ) (Stalvey et al., 1999), LSQ assesses the extent of an older person’s mobility and is useful for evaluating interventions designed to enhance mobility.
- **Exit Questionnaire** – (administered only at evaluations occurring directly after completion of training). This non-disease specific instrument consists of items which ask whether the participant enjoyed the classes, whether they would continue, whether they notice improvement in various aspects of physical wellbeing, and a section for open-ended responses (Hackney et al., 2007a, 2007b, Hackney & Earhart, 2009a, 2009b, 2009c, Hackney& Earhart NNR, 2010, Hackney & Earhart, J Nerv Ment Dis, 2010). Standardized measures that capture the same constructs do not exist.
- For those with PD only, the following questionnaires will be administered:
  - **Freezing of Gait questionnaire**- subjective evaluation of perception of freezing of gait phenomenon in the previous week (Giladi et al., 2001)
  - **PDQ-39**- health-related quality of life measure for persons with PD that is validated and widely used.

#### **Participation**

- **Impact on participation and autonomy scale**- This is a self-report measure and includes multiple domains of participation along with a strong focus on an individual's autonomy in his/her choices for daily activity participation.
- **Physical Activity Scale for the Elderly**- This scale is an easily administered and scored research instrument that measures the level of physical activity in individuals aged 65 years or older.

#### **Cognitive function**

- **Brooks spatial memory task** -The participant is asked to visualize a 4x4 matrix in which the location of numbers 1 through 8 is described. Next, the participant is requested to repeat the numbers' location. Participants practice with three instructions and progress up to 8 instructions. All levels are completed regardless of errors in performance and percentages correct (out of 50) will be used for analysis.
- **Body Position Spatial Task**- We found no standardized measure of whole body spatial working memory, i.e., knowledge of spatial position and ability to navigate in a remembered path. Modeled after the Corsi Blocks , the PI developed this task. Instead of pointing to a spatial path of blocks, participants are asked to step in a spatial arrangement. The examiner verbally and visually demonstrates random combinations of 5 possible moves: step forward, step left, step right, quarter turn left, and quarter turn right. The examiner begins with 2 moves and progresses up to a maximum of 9 moves, (maximum correct: 16) with 2 trials per level. Participants continue to the next level if one trial is correctly performed. The test ends when participants miss both trials of a level. Span length and number of correct trials are considered for analyses.
- **Corsi Blocks task**- (Kessels et al., 2008), this is a standardized, valid and reliable test of visuospatial ability
- **California Verbal learning test** (to rule out other possible cognitive deficits not found by the MoCA)
- **Wisconsin card sorting test** (64 cards) (Kongs et al., Western Psychological Services) - This test will probe the effects of EG training because participants will be required to respond and alter their decisions based on cues. The following will be outcome variables: Perseverative errors (fewer errors indicate better ability of the patient to switch to a new concept); Failure to maintain set (fewer failures indicate better ability to sustain course of action); Number of sorts (greater sorts indicate better concept formation.)
- **Color Word Interference Test** (Delis-Kaplan Executive Functions System) - Based on the Stroop, this test of executive function and attentional flexibility will also be administered to test the effects of EG training, because participant needs to inhibit their own responses and examine carefully the message that is being given, in spite of sometimes misaligning information.
- **Tower of London**- This test of organizational planning and decision-making will be administered to explore the cognitive effects of IG training, because the test requires the participant to organize, and plan. We will use the Cambridge Neuropsychological Test Automated Battery-Tower Of London, because of impairments in individuals with PD.100 The participant will be shown two displays of three colored balls. The participant is required to rearrange the balls in the bottom half of the screen to match the arrangement in the top half of the screen. The outcome measures are: number of successfully completed problems, number of problems completed in the minimum number of moves and the total score.

Table 2 provides a synopsis of the measures used in this study.

**Table 2: Outcome measures of motor, psychosocial and cognitive function**

Motor function	Instrument/scale
Functional mobility, strength	6-Minute Walk Test; single and dual task Timed Up and Go, Four-square Step Test, 30 s Chair Stand test
Preferred, backward, fast gait	GaitRite walkway (CIR Systems)

Postural control/ Fall Risk	Dynamic Gait Index, Berg Balance Scale, Fullerton Advanced balance scale
Handedness	Edinburgh Handedness Inventory
Psychosocial function	Instrument/scale
Depression	Geriatric Depression Scale-15; BDI-II
Incontinence- self report	ICIQ
Balance confidence	Activities Balance Confidence Scale
Quality of life	Life Space Questionnaire, Incontinence IQ, Short Form 12  PD ONLY: PDQ-39; Freezing of Gait
Participants' program enjoyment/satisfaction (Immediately post-training only)	Exit questionnaire- Evaluates participant satisfaction with physical activity programming, (Hackney & Earhart, in press ).
Self-report measure encompassing multiple domains of participation; a strong focus on an individual's autonomy in his/her choices for daily activity participation	Impact on Participation and Autonomy questionnaire
Participation in physical activity amongst older adults	Physical Activity Scale for the Elderly
Cognitive function	Instrument/scale
Spatial ability span	Brooks spatial working memory task (Brooks, 1967)
Body-position spatial ability span	Body position spatial task
Level achieved, trials completed	Corsi blocks
Verbal memory	California Verbal Learning test
Executive function, task switching, response to cues	Wisconsin card sorting test
Task switching, inhibition, attentional flexibility	Color Word Interference Test
Planning, initiation, procedural learning	Tower of London
Procedural learning	Serial reaction time task

## Screening

All participants will be screened for general health with a Project Health Questionnaire. All procedures will be videotaped. We will screen for both PD-related and non-PD related impairments that could compromise the study's results. Therefore, while all outcome measures and scans will be performed in both the ON and the OFF state, mental status, sensory impairments, and depression will be *IRB 60613 Motor Training in PD*

Study Version 6/14/16

screened during optimal performance conditions: the ON state. However, we will assess disease severity in both ON and OFF states because some outcome measures could be confounded by antiparkinsonian medications. We will also assess disease severity before all outcome measure evaluations.

Mental status: We will exclude individuals with known diagnoses of dementia or vascular cognitive impairment, and screen for mental status with the Montreal Cognitive Assessment (MoCA), which has been recommended by the Parkinson Study Group. We expect to exclude some individuals who pass the MoCA yet have severe primary memory deficits, possibly because of a PD/Alzheimer's disease overlap. Therefore, we will also administer memory testing with delayed recall on the California Verbal Learning Test.

Disease Severity: A qualified and experienced rater, blinded to study purposes, will rate participants with PD for disease severity with the Movement Disorders Society Unified Parkinson Disease Rating Scale Motor Subscale III(UPDRS) in videotaped assessments. Participants must have Hoehn & Yahr staging II-III. Participants will be evaluated for disease severity with the UPDRS at the beginning of all evaluations. Participants will also complete the Freezing of Gait questionnaire, a subjective evaluation of perception of freezing of gait (FOG) in the previous week. Participants will be considered "freezers" if they answer > 1 on item 3 of the FOG questionnaire, which indicates freezing frequency of more than once per week.

Sensory impairment: To screen for sensory impairments that could affect movement, we will screen for peripheral neuropathy, vision and hearing. We will screen for **peripheral neuropathy** with the 5.07-10g Semmes Weinstein monofilament method and the vibration on-off method in a clean open space, using established criteria. Participants will be screened for best corrected/aided **visual acuity** better than 20/70 in the better eye (World Health Organization International Classification of Disease-10, 2006); Measurement will be performed with intake screening & chart review. [name] will administer the Early Treatment in Diabetic Retinopathy Study Acuity test. Given the role that auditory cues will play in both evaluation (scanning will employ an auditory cue) and treatment (tango dance employs music), we will also screen participants for adequate **hearing**.

Depression: Participants will be screened for untreated depression with the BDI-II, recommended by the American Academy of Neurology, and suitable for screening individuals with PD. A cutoff of 18 is reliable for distinguishing individuals with PD with significant depression. If participants are excluded for depression, but then receive treatment, they may be rescreened and considered for study recruitment.

Ongoing screening for fMRI: Participants will be screened with standard procedures for fMRI eligibility during an initial telephone screen. Then, before every scanning session, participants will answer a standard questionnaire to insure safety during the procedures and adherence to fMRI inclusion and exclusion criteria. Participants will be evaluated for disease severity with the MDS-UPDRS at the beginning of all evaluations.

### **Specific Aim 1: Determine neural correlates of internally guided and externally guided foot-tapping in veterans with and without PD.**

**Rationale:** We will examine brain activity involved in internally and externally guided lower limb movement, in order to characterize circuitry, which we hypothesize will be targeted by the IG and EG training proposed in Aim 2. Adapted tango has been shown to improve gait and mobility measures;

[figure not shown]
therefore, adapted tango should include the recruitment of neural systems of lower limb control. Foot-tapping involves lower limb control, and is an action that occurs in adapted tango training. Foot-tapping is also a measure of motor dysfunction on the UPDRS, and its circuitry has been investigated in fMRI studies of healthy controls and individuals with PD. However, lower limb neural control of circuitry involved in externally and internally guided movements is not well studied. As such, we will use foot-tapping to provide a window into brain activation during IG and EG lower limb movements. With Aim 1, we seek to identify circuits and structures involved in IG and EG lower limb movement, in veterans with PD in comparison to age-matched controls. We believe that IG and EG lower limb circuitry will have similarities to that observed with finger tapping tasks because Keele et al (1985) demonstrated that finger tapping, forefoot tapping and heel tapping are highly correlated. Therefore, we **hypothesize** that during **IG tasks**, the STC (posterosuperior putamen, ventral anterolateral thalamus, rostral supplementary motor area (SMA), and primary motor cortex) will be activated in controls. During **EG tasks** the CTC (cerebellum Larsell lobules IV, V, and VI), ventral posterolateral thalamus, primary somatosensory cortex, and the ventral premotor cortex) will be more active relative to rest in controls. We predict that in PD patients, during IG tasks, both the STC and CTC circuits will be activated, while only the CTC circuit will be functionally activated during EG tasks.

#### **Rationale for hypothesized areas within circuits during IG and EG tasks:**

For **IG networks**, we expect to see activation in the following areas: the posterosuperior putamen, because dopamine depletion in PD most adversely affects this part of the putamen, which is also less functionally connected to important motor structures i.e., the rostral SMA, in individuals with PD relative to controls; the ventral anterolateral thalamus because of its projections from the basal ganglia and because it is part of the IG network outlined by Lewis et al. (2007) and Sen et al. (2010); the rostral SMA, because of its involvement in motor preparation and initiation, and its activation during foot flexion/extension; the primary motor cortex, because of its activation during foot movements and IG tasks in people with PD.

For **EG networks**, we expect to see activation in the following areas: Larsell lobules IV, V, and VI of the cerebellum, because these areas were functionally activated during cued foot movement in controls; the ventral posterolateral thalamus, because of its projections from sensory areas and cerebellar inputs, and because it is part of the circuit outlined by Lewis et al. (2007) and Sen et al. (2010); the primary somatosensory cortex, for its involvement in cued movement, both tactile and visual, with its expected localization being medial for foot movement; the ventral premotor cortex, because of its involvement in decision making based upon somatosensory signals, activity that mirrors the actions of viewed subjects, and because of its response to externally cued stimuli.

#### Specific Aim 1: Experimental Plan

[figure not shown]

**FMRI Data acquisition for Aim 1:** 24 older veterans with PD and 24 veterans without PD will be scanned for approximately 1 hour inside the scanner. MR images will be acquired on a 3T Siemens Magnetom Trio TIM scanner with a 32-channel receiver array head coil. BOLD fMRI scans will be acquired with a conventional Echo Planar Imaging (EPI) sequence with Field of View (FOV) =220 IRB 60613 Motor Training in PD

Study Version 6/14/16

mm, TR/TE/FA = 2000 ms/24 ms/80°; forty-seven 3mm sagittal slices (no slice gap); 3mm x 3mm in-plane resolution, and band width of 2414 Hz/pixel; Parallel Imaging: GRAPPA factor 2, 24 phase encode reference lines. Prospective real-time motion correction  will be used with all EPI fMRI scans to minimize motion artifacts. A whole-brain 3D T1-weighted MPRAGE sequence (FOV=230 mm; TR/TI/TE/FA=2250 ms/900 ms/3 ms/9°; 0.9mm x 0.9mm x 1mm resolution) will provide anatomic detail. All scans will be acquired with parallel imaging: (GRAPPA; acceleration factor = 2; 24 (for EPI) and 36 (for MPRAGE) phase encoding reference lines). A Biopac (Goleta, CA) respiration belt and finger pulse oximeter will be used to acquire physiological waveforms time-locked to fMRI acquisition. Activation paradigm design: Participants with PD will be scanned while ON and OFF their anti-parkinsonian medication at least 12 h after their last dopaminergic medication, a functionally defined “OFF”;  thereby maximizing the ability to see a therapeutic effect. Participants will spend about 1 h total in the scanner. The scanning protocol, including time spent in the scanner, will be clearly explained to all participants, and it will be verified that every participant fully understands and is prepared for the scanning procedure. Standard operating procedures for fMRI involves checking with participants throughout to make sure they are comfortable with scanning procedures and participants are removed from the magnet at any point should they require it. The experimenter or technologist will have frequent verbal contact with the participant throughout the scanning session to assure participant comfort.

For ~20 minutes, participants will perform IG and EG sequences of foot-tapping movements inside the scanner using established methods . As such, the task will involve unilateral ankle dorsiflexion, to a maximum of 30° in a wooden apparatus with movements blocked by IG or EG condition. Participants will be provided foam padding and towels to restrain head motion. Participants’ knees will be flexed to approximately 135° with a soft roll under the knees. An assistant will verify task performance timing and amplitude, as well as monitor for synkinesia from the other limb. If the patient is unable to keep the other limb still, the data will be excluded. Based on pilot scans that we recently collected in 15 individuals with stage II and III PD, we expect 20% attrition for excessive head movement. However, these participants were scanned while ON meds, which generally increases the presence of dyskinesia. Because we will a) test participants OFF meds, b) screen for excessive head and lower limb tremor, and c) target recruitment in order to account for 20% attrition, we expect to retain a sample size that will allow us to detect effects and make meaningful comparisons. Ankle range of motion will be recorded with an MR-compatible potentiometer and amplitude will be averaged over each condition. Absolute timing error will be determined by the potentiometer also, by comparing the timing of every other change in acceleration, with the ideal timing sequence. Thus, the time course of changes in acceleration will be effectively considered the timing of the participants’ taps. Error will be averaged from the accumulated absolute value of the tapping errors which either over- or under-shoot the ideal timing. Tapping will occur at a frequency of 0.5 - 2 Hz, *IRB 60613 Motor Training in PD*

Activation paradigm: In 30 s EG blocks, participants will tap their feet in response to externally provided auditory cues. In 30s IG blocks, participants will tap their feet in pre-learned rhythms. 21 s of rest will occur between IG and EG blocks. There will be 5 blocks per condition

given that individuals with PD demonstrate marked tapping performance deterioration above 2 Hz, in terms of increased movement rate, decreased amplitude and loss of movement phase.

**IG and EG foot-tapping tasks:** Before entering the scanner, participants will be given approximately 20 minutes to learn one of three unique, 6-s rhythmic sequences of IG and EG foot-tapping. These rhythmic sequences will be similar to those learned during both the IG and EG trainings, i.e., slow and quick beats arranged in different sequences to form differing rhythmic pattern (See “Adapted Tango”). In the EG condition, foot-tapping will be paced by auditory cues from MR-compatible headphones. In the IG condition, because the actual response rate will vary slightly by participant, we will quantify timing interval consistency based on each individual's tap-by-tap deviation from an established “ideal timing” rhythm that will be instructed before entering the scanner. We will determine each participant's average IG response rate (in taps/s) across all IG task blocks in the session, and then calculate the expected amount of time between sequential taps (quick or slow) based on this rate. We then will calculate the deviation from this expected tap time for each pair of sequential foot taps. Finally, we will average all deviations to determine the amount of variation there is in a participant's tapping pace within the scanning session.

In the scanner, participants will be asked to repeat the given foot-tap sequence continuously for 30 s/block. Sequence order will be counterbalanced across participants. IG and EG movement blocks of 30 s will alternate with 21 s of absolute rest. There will be 5 movement blocks and 6 rest blocks per foot, per condition (IG or EG). Both legs will be tested separately. See diagram illustrating the activation paradigm.

**fMRI Data Preprocessing for SA1:** Data will be processed using Statistical Parametric Mapping Software (SPM8; Wellcome Department of Imaging, Neuroscience, London, UK). Preprocessing steps include head motion correction, co-registration of functional and structural data within sessions, and co-registration of structural data across sessions. Each individual subject's structural and functional data will be spatially normalized to the SPM-standard T1 template, which is in Montreal Neurological Institute (MNI) space. Spatially normalized images will be smoothed with a 5mm full-width-at-half-maximum (FWHM) Gaussian kernel. Low frequency drifts will be removed with a temporal high-pass filter (0.006 Hz). The fMRI scans will be acquired with prospective real-time motion correction. This sequence will correct for volume-to-volume (image-to-image) motion less than 3mm by updating the gradients real-time during scan acquisition. If for a given volume the residual motion after motion correction (estimated as the maximal voxel displacement by the image registration algorithm) is more than 3mm (one voxel dimension) that volume will be discarded during analysis and treated as missing at random (MAR) during statistical signal processing. If more than 10% of the volumes in the fMRI time-series have to be discarded due to the criteria mentioned above, the subject data will likely be discarded from analyses. In previous studies examining a similar foot-tapping task while OFF, PD head movement ( $0.46 \text{ mm} \pm 0.26 \text{ mm}$  in either direction) was not much different from controls ( $0.56 \text{ mm} \pm 0.26 \text{ mm}$ ). However, we will recruit for 20% attrition, to account for unsuitable data.

**Specific Aim 2: Determine the effect, in veterans with PD, of internally guided versus externally guided training compared to a behavioral control on: 1) mobility, and 2) whether improved mobility and foot-tapping performance after training correlate with changes in activation and resting-state functional connectivity patterns in IG and EG foot-tapping networks.**

**Rationale:** As outlined in Background, there are differences in IG and EG training that may lead to distinct effects upon mobility; therefore, Aim 2 will tease out the relative effectiveness of IG and EG

[figure not shown]
adapted tango training for functional gains in mobility. Aim 2 will also determine whether improved mobility and foot-tapping performance after training correlate to changes in activation and resting state functional connectivity (RSfc) patterns in the IG and EG foot-tapping networks identified in Aim 1. Because we hypothesize that IG and EG adapted tango will target their respective foot-tapping networks, we expect improvements in each to correlate to changes in activation patterns in the corresponding network. Specifically, improved functional performance after IG training will lead to increased activation within the STC network while improved functional performance after EG training will lead to increased activation within the CTC network.

We will also determine how RSfc in the IG and EG foot-tapping networks is affected by training. A network perspective of PD is essential to understand the pathophysiology of the disease because the neurochemical alteration in the basal ganglia propagates throughout many dense striato-cortical connections, altering the activity in each successive brain region and because the pathology is widely distributed. RSfc MRI allows investigation of large-scale functional networks at whole-brain level based on temporal correlation of spontaneous fluctuations in the BOLD signal at a low frequency (<0.1 Hz). Few studies have used this technique to characterize network activity in PD. Previous research has shown abnormal patterns of RSfc of motor planning in premotor areas and execution networks (motor cortex) in PD patients. By scanning the same participants before and after training, we hypothesize that if we observe improved foot-tapping after IG training, we will see increased STC connectivity and if we see improved foot-tapping after EG training we will see increased CTC connectivity. We postulate no changes will be noted in IG and EG foot-tapping networks after training in the behavioral control group.

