## 7. Statistical Analyses

**Power Analysis for Specific Aim 1:** We anticipate that 20 participants in each group (total n=40) will be necessary to detect an adequate effect size at 80% power based on studies conducted to determine reasonable sample sizes for fMRI studies. Twenty-four participants per group will be recruited to accommodate 20% attrition. Analysis of variance (ANOVA) will be used to determine and distinguish circuits involved in IG and EG foot-tapping networks in participants with and without PD. The ANOVA will be sensitive to between subjects effect sizes of  $f=0.45$  ( $F_1, 38= 4.098$ ), with a power of 0.80 at  $\alpha=.05$ .

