### **Statistical Analysis Plan for Aim 1**

- **Participant characteristics:** Descriptive statistics will describe groups, including disease severity and duration for those with PD. T-tests will compare means (e.g., age, mental status) of participants with and without PD. Data analyses will be completed in SPSS (v. 19).
- **Functional performance measures:** Foot-tapping absolute timing error and average amplitude will be compared between groups with t-tests. These measures will also be correlated to fMRI data.
- **fMRI Brain Activation Analyses:** Following preprocessing and normalization to standard space, activation maps for the IG and EG tasks versus rest will be determined for each subject on a voxel by voxel basis. Regressors of interest will model IG and EG blocks of foot movement for each limb separately. Head motion parameters will be included as additional regressors. A similar approach has been used previously in PD. First level contrast maps (betas) for the IG and EG tasks versus rest derived in each subject will be submitted to a second-level, random-effects analysis with subject as a random factor. Second-level t-maps will be thresholded at  $p <.05$ , corrected for multiple comparisons using the false discovery rate (FDR) method. These activation maps will be used to define circuitry for IG and EG foot-tapping. Average percent signal change for the IG and EG tasks (relative to rest) for each participant will be extracted from the centers of gravity of the activated regions and submitted to hierarchical regression analyses to determine whether they correlate with behavioral measures (absolute timing errors and average amplitude of foot-tapping). Disease severity and duration of illness will be covariates for individuals with PD. **The primary outcome measure will be average percent signal change** for the IG and EG tasks (relative to

rest) to determine and distinguish circuits involved in IG and EG foot-tapping networks in participants with and without PD.

## Power Analyses for Aim 2

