## Statistical Analysis Plan for Aim 2, Hypothesis 1, 2 and 3:

- **Participant demographics:** Descriptive statistics will characterize groups. One-way ANOVA will determine differences, if any, between groups on baseline measures.
- **Behavioral Outcome measures:** A 3 group (IG, EG, BC) x 3 time (pre, post test, follow-up (1-month later)) RM ANOVA will be used to detect main effects. Appropriate post hoc tests will be used to determine within- and between-group differences,  $p<0.05$ , for **BBS, the primary outcome** measure upon which Aim 2 is powered. Statistical tests run on all secondary variables will be corrected for multiple comparisons.
- **Brain Activation Analyses for Aim 2, Hypothesis 2:** Similar to Aim 1 procedures, average percent signal change for IG and EG tasks (relative to baseline) for each participant will be extracted from the centers of gravity of the activated regions and submitted to hierarchical regression analyses to determine whether they correlate with behavioral measures (foot-tapping absolute timing errors and average amplitude). Disease severity and PD duration will be covariates. To determine the effects of time and training status we will submit the percent signal change to a 3 group (IG, EG and BC) X 2 time (pre, post) RM ANOVA. Post-hoc analyses will be corrected for multiple comparisons. The **primary outcome** will be t-contrast maps and effect size maps from ANOVA, which will be evaluated for changes in STC and CTC circuits.

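### Each participant taps one of three rhythms, but no tapping or activation model includes rhythm; the cost is mainly precision in the Aim 1 PD-versus-control comparisons

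*Combined protocol and SAP*

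**What the plan says.** All references are to the combined protocol and SAP.

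- **Task (section 5, Specific Aim 1: Experimental Plan, IG and EG foot-tapping tasks).** Before scanning, "participants will be given approximately 20 minutes to learn one of three unique, 6-s rhythmic sequences of IG and EG foot-tapping". The rhythms consist of "slow and quick beats arranged in different sequences to form differing rhythmic pattern". Each participant repeats the assigned rhythm in every 30 s block. The same paragraphs add: "Sequence order will be counterbalanced across participants".
- **Aim 1 power (section 7, opening paragraph).** The sample size is justified as follows: "We anticipate that 20 participants in each group (total n=40) will be necessary to detect an adequate effect size at 80% power". The detectable between-group effect is then put at f = 0.45, for a critical F(1,38) of 4.098, power 0.80 and alpha 0.05.
- **Aim 1 analysis (section 7, Statistical Analysis Plan for Aim 1).** "Foot-tapping absolute timing error and average amplitude will be compared between groups with t-tests". The first-level model has IG and EG blocks by limb plus head motion. The regressions of signal change on tapping performance name disease severity and duration as the only covariates, for participants with PD.
- **Aim 2 activation (section 7, Statistical Analysis Plan for Aim 2).** The signal-behaviour regressions again name only severity and duration. For training effects, "we will submit the percent signal change to a 3 group (IG, EG and BC) X 2 time (pre, post) RM ANOVA".
- **Aim 2 task and allocation (section 5).** The Aim 1 paradigm is reused. Whether a participant keeps the same rhythm at each scan is not stated, and randomization is not described as stratified by rhythm.

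**The concern.** Read plainly, rhythm is a between-participant factor with three levels that the design itself introduces. There are reasons to expect it to matter. Two quick beats equal one slow beat, so 6 s rhythms can differ in number of taps as well as in pattern. The protocol also limits tapping to 0.5–2 Hz because performance in PD deteriorates above 2 Hz.

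Three consequences follow for Aim 1 if rhythm affects signal change, timing error or amplitude:

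1. Its variance remains in the error term of the PD-versus-control comparisons.
2. If the rhythms fall unevenly between PD and controls, the group difference carries part of the rhythm difference, and nothing in the analysis removes it.
3. In the regressions linking signal change to timing error and amplitude, rhythm can act on both sides and produce a correlation that has nothing to do with PD circuitry.

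The third point also applies to the corresponding Aim 2 regressions. At stake are the precision of the Aim 1 imaging contrast and the interpretation of the signal-behaviour correlations.

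**Working it through.** **Inputs from the documents.** Evaluable n = 20 + 20 = 40; f = 0.45; alpha = 0.05; three rhythms, one per participant; 24 recruited per group.

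**Assumption.** The share of within-group variance explained by rhythm, R², is not given. The range 0 to 0.20 is shown.

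**Step 1: reproduce the plan's figure.** Noncentral F with λ = f²N = 0.45² × 40 = 8.10 on 1 and 38 df. The critical value is 4.098, as stated. Power is 0.792 against the stated 0.80, so the figure is reproduced. A 38-df error term (40 − 2) leaves nothing for rhythm.

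**Step 2: add rhythm as a fixed factor.** Error df = 40 − 2 − 2 = 36. Residual variance is multiplied by (1 − R²), so λ = 8.10/(1 − R²). This assumes rhythm is balanced within PD and within controls.

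| R² (assumed) | λ | Power, F(1,36) | Detectable f at 80% power |
|---|---|---|---|
| 0 | 8.10 | 0.791 | 0.455 |
| 0.05 | 8.53 | 0.811 | 0.444 |
| 0.10 | 9.00 | 0.831 | 0.432 |
| 0.20 | 10.13 | 0.872 | 0.407 |

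Against 0.792, the change is −0.1, +1.9, +3.9 and +8.0 percentage points.

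**Step 3: leave rhythm out.** What happens depends on how it was assigned. The two cases below are alternatives and their effects do not add.

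*Case A: balanced within each group, not modelled.* The group means are protected but the error estimate is too large. In simulation with 20 per group, the t-test's type I error is about 0.044, 0.039 and 0.029 for R² of 0.05, 0.10 and 0.20. Its power at d = 0.90 is about 0.796, 0.805 and 0.816. The model with rhythm gives 0.811, 0.831 and 0.872, so about 1.5, 2.6 and 5.6 points come from modelling rhythm once it is balanced.

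*Case B: balanced only over all participants, independent of group.* Type I error stays at 0.049–0.051 and power at about 0.79. Imbalance between groups is then common:
- With 48 participants, 16 per rhythm and 24 per group, the PD and control counts for some rhythm differ by 4 or more in about 62% of allocations and by 6 or more in about 27%.
- With 20 per group, the largest count difference has a median of 3 and is 5 or more in about 32%.
- In the 20 v 20 case, the 95th percentile of the resulting chance group difference is about 0.15, 0.21 and 0.30 SD for R² of 0.05, 0.10 and 0.20, against a detectable d of 2 × 0.45 = 0.90.

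**Step 4: Aim 2 group × time.** Write a participant's signal at scan t as a person effect, plus a rhythm effect, plus group and time terms. If the rhythm is the same at pre and post, the additive rhythm effect subtracts out of the change. Only a rhythm-by-time effect, or a change of rhythm between scans, would remain.

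**The case against.** The other side has several fair points.

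- **The counterbalancing sentence is ambiguous.** With one rhythm per participant there is no order of rhythms to balance. The sentence may refer to the order of IG and EG runs, and the paradigm diagram is not available in the text reviewed. This stands. It is a reason to clarify the wording, but the absence of a rhythm term does not depend on it.
- **The design already limits rhythm effects.** All rhythms last 6 s, fill identical blocks and use the same quick and slow units. Timing error is measured against the ideal timing, and IG consistency is scaled to the participant's own rate. If one rhythm serves both conditions, an additive effect also cancels from IG versus EG within a participant. This stands and argues for a small R². It does not protect the PD-versus-control difference or the signal-behaviour regressions.
- **R² is assumed.** This stands. At R² = 0 there is no gain, and the cost is 0.001 in power.
- **F(1,38) is a sensitivity statement, not a full model.** True, but the analysis sections name other covariates and do not name rhythm.

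A reader might also infer three stronger things that the documents do not support. The first is that false positives are inflated; they are not if rhythm is independent of group, and Case A is conservative. The second is that rhythm differences pass directly into the Aim 2 change scores. Nothing says a participant's rhythm changes between scans, and a constant additive effect cancels. The third is that every analysis is affected. The Berg Balance Scale involves no tapping, and connectivity data are acquired at rest.

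**Conclusion.** The point holds as a matter of precision and interpretation, chiefly in Aim 1. Rhythm is set by the design and is missing from the percent-signal-change ANOVA, the t-tests on timing error and amplitude, and the signal-behaviour regressions of both aims. Balancing and modelling it would raise Aim 1 power by about 2 to 8 points for an assumed R² of 0.05 to 0.20, and by nothing if rhythm has no effect. Without balance within groups, the chance shift in the group difference would usually stay below about 0.15 to 0.30 SD over the same range. Possible confounding of the signal-behaviour correlations cannot be sized from the documents. No error in the validity of the group tests is shown. The point is a low-priority improvement.

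**What to change.** 1. State what is counterbalanced. Assign the three rhythms in balance within PD, within controls and within each Aim 2 arm. With 24 recruited per Aim 1 group this is 24/3 = 8 per rhythm; with 25 per Aim 2 arm, 9, 8 and 8.
2. State that each participant keeps the same rhythm at all scans, so that an additive effect cancels from the pre-post change.
3. Add rhythm (3 levels, fixed) to the Aim 1 percent-signal-change ANOVA. Replace the t-tests on timing error and amplitude with linear models containing group and rhythm. Add rhythm to the signal-behaviour regressions in Aims 1 and 2.
4. Restate the Aim 1 test as F(1,36).

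The cost is SAP wording, an assignment list and 2 error degrees of freedom (power 0.792 to 0.791 if rhythm has no effect). No additional participants or scans are needed.
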